## **BACKGROUND**

Within anesthesia, there are several modalities such as general anesthesia or locoregional anesthesia. General anesthesia refers to the use of intravenous or inhaled drugs to achieve hypnosis, anesthesia and analgesia of the patient to be operated on. However, the action of general anesthesia is systemic and entails numerous side effects such as nausea, vomiting, postoperative delirium, etc. Therefore, it is a technique that involves more interactions and complications with the patient's comorbidity and treatment (1).

Locoregional anesthesia is one of the anesthetic subspecialties that has prospered the most in recent decades, especially with the development of ultrasound as a nerve localization technique. This anesthetic modality began as early as the 19th century and includes central neuroaxial blocks as well as peripheral nerve blocks. These allow surgery to be performed with adequate analgesic, anesthetic and motor control of the surgical site with the advantage that the patient is conscious. It can be used as a single anesthetic technique or combined with general anesthesia to reduce analgesic requirements and its systemic side effects.

Neuroaxial blockade refers to the administration of local anesthetics (LA) in the vicinity of the spinal cord, either within the cerebrospinal fluid at the subarachnoid level or at the epidural level, to produce a sensory and/or motor blockade (1,2).

On the other hand, peripheral nerve blockade (PNB) consists of administering AL around the peripheral nerves or nerve plexus, external to the spinal column. According to the 10th International Classification of Diseases (ICD-10), this procedure is classified with the code 3E0T3CZ as: Block, Nerve, injection of anesthesia (3,4). They can be adapted to surgical needs and used for perioperative anesthesia or analgesia and for chronic painful processes. To perform them, knowledge of nerve anatomy including the brachial and lumbosacral nerve plexuses as well as the major peripheral nerves such as the median, musculocutaneous, ulnar and radial nerves in the upper extremity or the femoral, femorocutaneous, obturator, sciatic, sciaticopopliteal nerves in the lower extremity is required.

The most commonly used peripheral nerve blocks in anesthetic practice are the brachial plexus block with interscalene approach or with supraclavicular, infraclavicular or axillary approach for shoulder and upper extremity surgery. For lower extremity surgeries, the femoral, femorocutaneous, obturator, sciatic or sciatic-popliteal nerve block is used (2,5).

In recent times, the use of PNBs has increased because it has demonstrated an improvement in analgesic control according to the visual analog scale (VAS), a decrease in postoperative analgesia, postoperative nausea and vomiting, a shorter stay in the postanesthesia recovery unit and an increase in patient satisfaction (1,5-9).

Contraindications for peripheral nerve blocks are few and general, such as patient rejection, hemodynamic instability, local infection at the puncture site or allergy to the LA to be used. Possible complications of these techniques are peripheral nerve injury such as neuropraxia, axonotmesis or neurotmesis, vascular complications such as neuronal ischemia or hematoma, or neuronal, cardiovascular or systemic toxicity due to the use of LA (2).

In some countries there are national registries of anesthetic results; however, to date there are no published data of a registry of locoregional anesthesia techniques in Spain (5,10). Therefore, the benefit of this work is estimated to be very high with respect to the risk involved, since it involves the same risks of the usual anesthetic practice with the aim of reviewing this same clinical practice to evaluate its safety and to be able to compare it with international standards.

Therefore, this work will try to make the first description of the mode of use and complications of locoregional anesthesia carried out in a tertiary hospital with an anesthesia unit specialized in this type of techniques in our country. The purpose is to evaluate the current management and the evolution of our usual clinical practice in locoregional anesthesia.

## **INTERVENTION FRUG**

The investigational drugs in the study have been provided by the Pharmacy Service of the HUMS since they are medications used in the usual clinical practice of the ARTD Service.

### **TRADE NAME:**

- Chirocane® 1.25 mg/ml Injectable and infusion solution.
- Chirocane® 2.5 mg/ml Solution for Injection and infusion.
- Chirocane® 5 mg/ml solution for injection and infusion.
- Mepivacaine Braun 1% Solution for Injection EFG.
- Mepivacaine Braun 2% Solution for Injection EFG.
- Bupivacaine Hyperbaric B. Braun 1.25 mg / ml solution for injection.
- Bupivacaine Hyperbaric B. Braun 2.5 mg / ml solution for injection.
- Bupivacaine Hyperbaric B. Braun 5 mg / ml solution for injection.
- Lidocaine B. Braun 20 mg / ml solution for injection.

### **ACTIVE INGREDIENT:**

- Levobupivacaine 1.25 mg/ml Solution for Injection and for infusion.
- Levobupivacaine 2.5 mg/ml solution for injection and infusion.
- Levobupivacaine 5 mg/ml solution for injection and infusion.
- Mepivacaine 1% Solution for Injection EFG.
- Mepivacaine 2% Solution for Injection EFG.

- Bupivacaine Hyperbaric 1.25 mg / ml solution for injection.
- Bupivacaine Hyperbaric 2.5 mg / ml solution for injection.
- Hyperbaric Bupivacaine 5 mg / ml solution for injection.
- Lidocaine 20 mg / ml solution for injection.

PHARMACEUTICAL FORM: Solution for injection and infusion.

ROUTE OF ADMINISTRATION: Perineural administration through peripheral nerve block needle.

EXCIPIENTS: indicated in AEMPS data sheets (11-18).

All the drugs are authorized for marketing by the AEMPS, and will be administered according to the usual clinical practice of the ARTD Service, COT Service (11-18). They belong to the AL pharmacotherapeutic group (amides) with ATC code N01B B10 (Anatomical, Therapeutic, Chemical classification system). They consist of a colorless, clear solution for injection and infusion, available in 5 to 10 ml polypropylene ampoules (12).

All of them have been administered by an anesthesiologist specialized in the management of locoregional anesthesia and its drugs, according to the dosage established in the technical data sheets of the Spanish Agency of Medicines and Health Products (AEMPS). The therapeutic indication of the intervention studied is surgical anesthesia by PNB in adults (11-18).

All drugs have been administered perineurally by means of a BNP needle since this is the only way of administering a drug in locoregional peripheral nerve anesthesia. During dose administration, patient monitoring was performed and blood puncture prevention measures were taken according to standard clinical practice (12).

## **OBJECTIVES**

The primary objective of this study is to quantify the number and type of peripheral nerve blocks performed in the routine anesthetic practice of the Traumatology Anesthesia Unit of the Miguel Servet University Hospital. Secondary objectives are: to describe to assess the safety of peripheral nerve blocks in the routine anesthetic practice of the Traumatology Anesthesia Unit of the Miguel Servet University Hospital: number, severity and resolution of complications.

## **DESIGN**

This is a descriptive, observational, retrospective, single-center, retrospective study of a population-based sample of all patients who have undergone orthopedic and trauma surgery and who have undergone PNB, according to standard clinical practice, in the Traumatology Anesthesia Unit of the Miguel Servet University Hospital (Zaragoza, Spain).

The source of our population sample is all patients undergoing scheduled or urgent surgery by the COT Department of the HUMS and who underwent perioperative PNB by the ARTD Department's ATU.

The registration of the cases in this study was carried out at HUMS, where the generated database is kept. The data analysis was carried out in a cross-sectional manner with a retrospective follow-up of the sample.

Patient recruitment spans from January 01, 2011 to November 30, 2019. Cases have been recruited by convenience, during the perioperative process of patients in the surgical block of HUMS, up to a total of 13759 BNPs.

Follow-up after medication administration and BNP performance lasts until the present day. It is performed by the clinical evaluation of the services responsible for patient follow-up, see the COT Service, who does not redirect possible complications encountered in the operated patients.

The anesthetic and surgical procedures have been performed, according to standard clinical practice, in the multifunctional surgical block of the HUMS.

In this work, no biological samples were obtained from a care process and no specific test was performed.

During this work, 3 figures were involved: the PI, the ICs and the anesthesiology team. The team of anesthesiologists has been in charge of performing the interventional techniques of the BNP according to the usual clinical practice and which have been collected in the BD. They were also the ones who completed the CRD after performing the PNBS. The ICs have been those who have made the BD from the CRD of all the NIBPs performed. Finally, the PI will be responsible for the processing of the DB data.

This work has been carried out within the usual care activity of the ARTD Service's TCU and this practice has been followed in all cases.

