## **INCLUSION CRITERIA**

In order to be included in this study, patients had to meet all the following inclusion criteria:

1. Written informed consent in which the patient agrees to undergo anesthetic procedures: general, locoregional or local anesthesia (general informed consent of the ARTD Service of the HUMS for any anesthetic procedure).
2. To undergo scheduled or urgent surgery by the COT Service.

3.Have a peripheral nerve block technique performed by the Traumatology Anesthesia Unit (ATU) of the ARTD Service of the HUMS.

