## **STATISTICS**

Data were collected in Microsoft Excel tables and IBM SPSS Version 22 for Windows [under license from the University of Zaragoza]. For all analyses a statistically significant result is assumed if  $p < 0.05$ . The statistical analysis performed includes a descriptive and inferential analysis.

A descriptive analysis of the data will be performed: the qualitative variables (age, sex, etc.) will be presented by means of the frequency distribution of the percentages of each category and the quantitative variables studied (volume of local anesthetic, concentration of local anesthetic, etc.) will be explored with the Kolmogorov-Smirnov test of conformity (goodness-of-fit test to a normal distribution). Likewise, indicators of central tendency (mean or median) and dispersion (standard deviation or percentiles) will be given.

The degree of association between variables will be examined using graphical (scatterplot) and analytical (simple correlation coefficient) methods. The interpretation of the intensity of the relationship will be performed according to the criteria established by Gerstman (2015) and Martínez-González and et al. (2014) (20,21).

Regarding the bivariate analysis or comparison between two variables (factors), the association between the factors will be investigated by means of hypothesis contrast tests. In case both variables compared are qualitative, by means of a comparison of proportions with chi-square or Fisher's exact test. If one of them is quantitative, a comparison of means will be made by means of Student's t-test, ANOVA, and if they do not follow a normal distribution, the Mann-Whitney U test or the Krustal-Wallis test. Likewise, a bivariate correlation (Pearson's correlation coefficient) will be carried out when both variables are quantitative or, if the application conditions are not met, a Spearman's correlation.

As for the multivariate analysis, to study the relationship of each variable controlling for the possible effect caused by third variables, the analysis will be completed by regression models.

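### The sample is counted in blocks with no patient count, and the planned tests assume independent rows: if patients contribute several blocks, p-values are modestly off and need a patient-clustered analysis where events are not sparse

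*Combined protocol and SAP*

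**What the plan says.** The DESIGN section of the combined protocol and SAP defines the sample as a "population-based sample of all patients who have undergone orthopedic and trauma surgery and who have undergone PNB", and the inclusion criteria also apply to patients ("Have a peripheral nerve block technique performed by the Traumatology Anesthesia Unit"). The only size given is in blocks: "up to a total of 13759 BNPs", recruited from 1 January 2011 to 30 November 2019. Scheduled and urgent surgery both qualify. Neither the design nor the eligibility criteria restrict a patient to one block or one operation.

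The row unit of the database is not stated. DESIGN points towards blocks: the anesthesiologists "completed the CRD after performing the PNBS", and the collaborating investigators "made the BD from the CRD of all the NIBPs performed". The abbreviation in that last quote is not in the glossary; it is read here as blocks.

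Both aims under OBJECTIVES are descriptive: the number and type of blocks, and safety as "number, severity and resolution of complications". STATISTICS goes further: "The statistical analysis performed includes a descriptive and inferential analysis". At p < 0.05 it names chi-square, Fisher's exact, Student's t, ANOVA, Mann-Whitney, Kruskal-Wallis, Pearson and Spearman, followed by regression models of unspecified type. It mentions neither repeated blocks nor clustering.

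PROCESSING OF PERSONAL DATA says that each patient has a study identification code. It also calls the database anonymous.

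**The concern.** Every bivariate test named under STATISTICS assumes, in its standard form, that rows are independent. A patient may have more than one block at one operation, or return for another within almost nine years. Two blocks in one patient share age, sex and comorbidity, and may share an outcome. If they are analysed as two independent rows, the standard error for a patient-level factor is too small when the correlation is positive. For a factor that differs between a patient's own blocks, such as block type, it can be too large. The regression models could deal with this, but the plan neither provides for it nor rules it out.

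What is at stake is the p-values in the association analyses, and any confidence intervals that are added, although none are planned. A second matter is labelling: a complication rate per block can be misread as a risk per patient.

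**Working it through.** **Inputs.** From DESIGN: 13,759 blocks. From STATISTICS: significance level 0.05, taken as two-sided. The documents give neither the share of patients with more than one block nor the intracluster correlation (ICC), so both are assumed. The figure of 13,759 is a count, not a calculated sample size, so there is no power calculation to reproduce.

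**Patients behind the count.** If a share f of patients has two blocks and the rest one, the number of patients is 13,759/(1 + f): 12,508 for f = 10%, 9,828 for 40%, and about 6,880 for all.

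**Patient-level factor.** With m the number of blocks per patient, the design effect is DEFF = 1 + ICC × (Σm²/Σm − 1). Here Σm²/Σm = (1 + 3f)/(1 + f), so the bracket is 0.182, 0.571 and 1.0. The actual error rate is 2 × [1 − Φ(1.96/√DEFF)].

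| Patients with two blocks | ICC 0.05: DEFF, alpha | ICC 0.2: DEFF, alpha | ICC 0.5: DEFF, alpha |
|---|---|---|---|
| 10% | 1.009, 0.051 | 1.036, 0.054 | 1.091, 0.061 |
| 40% | 1.029, 0.053 | 1.114, 0.063 | 1.286, 0.084 |
| all | 1.05, 0.056 | 1.2, 0.074 | 1.5, 0.110 |

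With one block per patient, or ICC 0, alpha is 0.05.

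**Which part of the table is credible for complications.** After an event on the first block, the risk on the second is p + ICC × (1 − p). At an assumed p = 1% this is 6%, 21% and 50.5% for ICC 0.05, 0.2 and 0.5. The last would need something like one event copied to both rows. If an event is entered on only one of a patient's two rows, the variance ratio is 0.98/0.99 and alpha is 0.049, so there is no inflation. The relevant range is therefore about 0.051 to 0.063 (10% to 40% with two blocks, ICC 0.05 to 0.2). A simulation of a 1% outcome over that range (6,000 replicates per setting, Monte Carlo margin about 0.006) gave 0.052 to 0.057.

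**Quantitative variables.** STATISTICS gives as examples "quantitative variables studied (volume of local anesthetic, concentration of local anesthetic, etc". These could correlate more strongly, or negatively if a total volume is split between blocks. At ICC −0.2, alpha is 0.046, 0.037 and 0.028 for 10%, 40% and all.

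**Factor that varies within a patient.** With one block of each type in every patient, DEFF = 1 − ICC, and alpha is 0.044, 0.028 and 0.006 at ICC 0.05, 0.2 and 0.5. The test is then too conservative.

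**Does clustering repair it?** For a 1% or a normal outcome and a binary patient-level factor, patient-clustered standard errors gave 0.045 to 0.054 in all 24 simulated settings. With sparse data it depends on the method. The following simulations used 13,759 blocks, 40% of patients with two, and no true effect:
- 1% rate, factor present in 5% of patients: ordinary chi-square 0.050 to 0.066; clustered Wald test of the risk difference roughly 0.08 to 0.09.
- 0.1% rate (about 14 events), factor present in 10%: chi-square 0.039 to 0.050; clustered risk difference about 0.25 to 0.27.
- On the logit scale the clustered test stayed at about 0.03 to 0.05. At a 0.1% rate, however, one group had no events in 25% to 53% of replicates (factor in 10% or 5% of patients), leaving no estimate.

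**Per block versus per patient.** With p = 1% and two blocks in every patient, the per-patient rate is 2p − [p² + ICC × p(1 − p)] = 1.940%, 1.792% and 1.495% at ICC 0.05, 0.2 and 0.5. The per-block figure is then 48%, 44% and 33% lower. Both are valid, but they answer different questions.

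**The case against.** The strongest reply is that neither premise is documented. The row unit is inferred, partly by reading an undefined abbreviation as blocks. One notebook could have been completed after all of a patient's blocks, and no repeat block is mentioned anywhere. This stands, and it makes the point conditional. It does not remove it: the plan gives a total in blocks, criteria in patients and no link between the two, and only the investigators can supply that link.

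The second reply is that the study is descriptive, with no named hypothesis and no decision that turns on a p-value. This also stands, and it limits the consequence to the inferential part of STATISTICS.

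The third is that the effect is small and has no fixed sign, and that for rare complications a careless remedy is worse than the test it replaces. The simulations bear this out, so a blanket instruction to cluster every test would be wrong.

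A reader might infer that 13,759 overstates the sample or that the safety results are invalid. The documents do not support this. The primary objective is a count of blocks, for which blocks are the right unit, and a per-block complication rate is a legitimate descriptive figure. A reader might also infer that the study code makes the correction automatic. The plan confirms a code per patient, but not that it is in the analysis file or stays the same across operations.

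**Conclusion.** The point holds conditionally and is minor. If rows are blocks and some patients contribute several, the named tests ignore within-patient correlation. Alpha for patient-level factors is then about 0.051 to 0.063 under the assumptions judged credible (10% to 40% of patients with two blocks, ICC 0.05 to 0.2). The values up to 0.110 need repeats in every patient and an ICC of 0.5, which is hard to credit for complications. For factors that vary within a patient the tests can be too conservative. The block count and the descriptive per-block complication rate stand. If every patient has one block, there is no problem. Correlation within anesthesiologist is a separate matter that clustering on patient does not address.

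**What to change.** 1. State the row unit, the number of patients and the distribution of blocks per patient.
2. Check that the study code is in the analysis file and links a patient's blocks across operations. If it links only within an episode, cluster on episode and state the limitation.
3. If there are repeats, use GEE or cluster-robust regression, clustered on that code, for quantitative outcomes and for non-sparse binary outcomes, with a logit link for the binary ones. This replaces the ordinary row-level tests in those analyses.
4. For rare complications, do not use a clustered Wald test of the risk difference. Collapse to one row per patient (any complication) and keep Fisher's exact test for patient-level factors, or report descriptively.
5. Label each complication rate as per block or per patient.

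The cost is SAP wording, one check of the code and a little more analysis work, with no new data if the code links blocks. Any confidence intervals for patient-level factors widen by √DEFF − 1, which is about 0.5% (√1.009) to 6% (√1.114) over the credible range. If the code does not link operations, some correlation stays unmodelled. If every patient has one block, a sentence saying so is enough.

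### Read literally, complications first recognised at surgical follow-up have no route into the database, so the safety count is a minimum

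*Combined protocol and SAP*

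**What the plan says.** The Objectives section makes safety the secondary objective, expressed as "number, severity and resolution of complications". The Background gives the wider purpose of reviewing the unit's practice as "to evaluate its safety and to be able to compare it with international standards".

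The Design section describes the data path in two steps. The anesthesiologists performed the blocks, and "They were also the ones who completed the CRD after performing the PNBS". The database followed from that: "The ICs have been those who have made the BD from the CRD of all the NIBPs performed". No other source for the database is named.

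On what happens afterwards, the same section says "Follow-up after medication administration and BNP performance lasts until the present day". It assigns this follow-up to the clinical evaluation of the responsible services, and adds: "see the COT Service, who does not redirect possible complications encountered in the operated patients". It also says "The data analysis was carried out in a cross-sectional manner with a retrospective follow-up of the sample", without giving a source, a procedure or a time window for that follow-up.

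The Statistics section does not mention ascertainment of complications. It defines no complication rate and no denominator.

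**The concern.** A complication count is only as complete as the route by which complications are recorded. Here the described record is made by the anesthesiologist after the block, while later observation of the patient belongs to another service that, as written, does not pass on what it finds. The Background lists peripheral nerve injury among the possible complications. If such an injury is first noticed at a surgical visit, the described path has no step that brings it, or its resolution, into the database.

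At stake is what the safety result means. Presented as the unit's number of complications, or divided by all blocks, it would be read as an estimate. On the described path it is a lower bound. The large number of blocks does not help: it narrows a confidence interval but does nothing for events that were never recorded.

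**Working it through.** **Inputs from the documents.** Objective: number, severity and resolution of complications (Objectives). Blocks registered: 13,759 (Design). Recruitment: 1 January 2011 to 30 November 2019 (Design). End of follow-up: the present day, with no date (Design). Expected complication rate, share recognised late, and share captured: none given. The 13,759 is a count of cases and not a calculated sample size, so there is no planned figure to reproduce.

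**Step 1: follow one late-recognised complication under each reading of the referral sentence.**

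| | Literal reading: surgical service does not refer | Slip: surgical service does refer |
|---|---|---|
| Seen by the anesthesiologist completing the CRD | No | No |
| Passed back to the anesthesia unit | No | Yes, if noticed and referred |
| Described step into CRD or database | None | None |
| Consequence for the count | Omitted; count is a minimum | Capture passive and undated; undercount possible |

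The retrospective follow-up mentioned in Design could fill the gap if it was a record review, but its source is not stated. The Glossary defines an acronym for the clinical history, yet the text available does not name that record as a data source.

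**Step 2: direction.** Let L be the share of complications recognised only later and not returned. Then

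recorded count = true count × (1 − L), with L ≥ 0.

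Any L above zero lowers the count, and lowers any rate over 13,759 by the same factor. Nothing in this path raises it.

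**Step 3: size.** The documents give neither the true count nor L, so the shortfall cannot be computed. What can be computed is the spread of potential follow-up: 30 November 2019 minus 1 January 2011 = 3,255 days, and 3,255 / 365.25 = 8.9 years between the first and last possible block. This shows that follow-up is not uniform. It does not measure bias, because the documents say nothing about when complications emerge.

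**Step 4: would a confidence interval reveal the problem?** This is an illustration only; the true rates (0.1% and 0.5%) and capture fractions are assumed. Recorded events = 13,759 × rate × capture, rounded. The limits are exact (Clopper-Pearson) over 13,759.

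| Assumed true rate | Capture | Recorded | Upper 95% limit | Includes true rate |
|---|---|---|---|---|
| 0.1% | 75% | 10 | 0.134% | yes |
| 0.1% | 50% | 7 | 0.105% | yes |
| 0.1% | 25% | 3 | 0.064% | no |
| 0.5% | 75% | 52 | 0.495% | no |
| 0.5% | 50% | 34 | 0.345% | no |
| 0.5% | 25% | 17 | 0.198% | no |

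Two rows turn on a single event: 53 instead of 52 gives an upper limit of 0.504%, which includes 0.5%, and 6 instead of 7 gives 0.095%, which excludes 0.1%. The table supports one modest statement: an exact interval allows for chance but not for missed events, and whether it still covers the truth depends on quantities the documents do not give.

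**The case against.** The strongest reply is that the key sentence is probably a translation error. The Design section shows other signs of it: the same technique appears under several acronyms, and the word retrospective is repeated within one description. The sentence sets out to explain how follow-up is done, and a statement that nothing is passed on defeats that purpose. In Spanish, *refers to us* and *does not refer* can differ by one letter. This is inference, not proof, but it is a reasonable one. It stands to this extent: the undercount is certain only on the literal reading, and only if some complications are first recognised late.

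A second reply is that the absence of a procedure is weak evidence in what looks like a condensed document. Completing the CRD after the block sets no closing time, so later entries are not excluded. The objective includes resolution, and a retrospective follow-up is mentioned, so later information was evidently intended. That also stands, but intention does not tell the reader what was captured. On either reading, no step into the database is described.

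A third reply is that no rate is planned. That is correct; a rate over all blocks is a possible use of the data, not a stated analysis. The count itself, however, is a stated objective.

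A reader might go further and infer that an international comparison would flatter this unit. The documents do not support that, because they do not say how the comparison sources followed their patients. Nor does the 8.9-year spread in potential follow-up by itself establish a biased count.

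**Conclusion.** The point holds in a limited form. As written, the CRD is the only described source of the database, and complications first recognised at surgical follow-up do not reach it. The count for the secondary safety objective is then a minimum, with a shortfall that cannot be computed from the documents. If the referral sentence is a slip, capture is passive with an undated end, and undercount is possible rather than certain.

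It would be too strong to say that the count is biased low whichever reading is right, or to attach a percentage to the shortfall. Both need facts that are absent: what the surgical service did, and when complications were recognised. The primary objective is untouched. Passive ascertainment is common in a retrospective design and is no fault in itself; what needs changing is a safety objective wider than the described data can support.

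**What to change.** 1. In Design, reconcile two statements with what was actually done: the sentence on referral by the surgical service, and the source and procedure of the retrospective follow-up. Replace the present day with the date that ends follow-up.
2. In Objectives and Statistics, define the safety result as complications recorded on the CRD, with the block total as denominator and exact 95% confidence intervals. State that severity and resolution are reported as far as the CRD holds them.
3. If any later-recognised complications were in fact captured, report them separately as a minimum count, with severity and resolution but no rate. If the literal reading is right, there will be none to report, and the report should say why.
4. Limit any comparison with international standards to events ascertained in a comparable way.

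The cost is small: wording in the protocol, SAP and report, with no new data collection. The downside is a narrower safety claim, confined to what was recorded on the CRD.
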